Pediatric Anxiety Rating Scale (PARS). The PARS is a clinician-rated scale assessing anxiety symptoms and the associated severity and impairment in children over the past week. The Symptom Checklist consists of 59 items assessing 7 categories of anxiety symptoms. Scores on the PARS Severity Scale range from 0 to 25, with scores >14 consistent with clinically significant levels of anxiety in youth with and without ASD. The PARS has good reliability and is sensitive to both pharmacologic and CBT treatment. 35

Pediatric Accommodation Scale (PAS). The PAS is a 16 item measure that assesses degree of reassurance needed, avoidance, parental involvement, and interference due to the child's anxiety over the past month.

Rage Outbursts and Anger Rating Scale (ROARS).⁹⁴ The ROARS is a 0 to 9 point scale measuring frequency, intensity, and duration of rage and anger. The participant does not have to do anything for this rating; the clinician rates it based on all available information.

Service Assessment for Children and Adolescents (SACA). A modified version of the SACA will be used. The SACA is a psychometrically sound parent interview about the broad use of mental health services.

Wechsler Abbreviated Scale of Intelligence (WASI).⁷⁶ The WASI is a short (four subtests), individually administered test of intelligence for children and adults ages 6 through 89. The four-subtests (Vocabulary, Block Design, Matrix Reasoning, Similarities) can be administered in about 30 minutes. It has demonstrated acceptable to excellent psychometric properties and is the recommended instrument when a quick and accurate estimate of general intellectual functioning if needed.

Youth Top Problems (YTP). 96 The Youth Top Problems approach is a well-validated evidence based assessment procedure that is sensitive to treatment response and found to provide information separate from that generated by standard checklist ratings of child symptoms 96. YTP scores have proven to be a valid measure of internalizing, externalizing, and total psychiatric symptoms among children involved in general mental health interventions when compared to much longer symptom checklists such as the CBCL and YSR, and are highly sensitive to treatment 96. To provide a clinical context for eliciting top problem reports from parents, a structured clinical interview pertaining to child psychiatric symptoms is administered to parents by a trained diagnostician. In this study, the diagnostic interview is the ADIS, to effectively focus parents' attention on anxiety symptoms. Then, parents are asked to state what problems that were just discussed are the most concerning to them. The diagnostician audiotapes this discussion and also writes the parents' responses down in their exact words.

Therapist Rated Measures:

Clinical Global Impression (CGI) Scales.⁹⁷ The CGI-Improvement is a 7-point rating of treatment response anchored by 1 ("very much improved") and 7 ("very much worse"). The CGI-Severity is a 7-point rating of severity anchored by 1 ("not at all ill") and 7 ("extremely ill").

Therapist Information Form (TIF).⁹⁸ The TIF is a 16-item therapist report form that assesses therapist demographics, training, practice experience, theoretical orientations and caseload associated with the study. This is completed at the first therapy session.

Youth Top Problems. The Youth Top Problems (YTP) ^{96 96 96 96 97 97} will be administered by the therapist at every session.

Parent-Rated Measures:

Autism Spectrum Rating Scales (ASRS). The ASRS is used to identify symptoms, behaviors and features associated with Autism Spectrum Disorders. Parents use a five-point Likert rating scale to report how often they observe specific behaviors in the domains of Social/Communication, Unusual Behaviors and Self-Regulation.

Childhood Anxiety Impact Scale - Parent (CAIS-P). 100

The CAIS-P is a parent report questionnaire of the impact of the child's anxiety on his/her psychosocial

functioning in certain situations.

Child Behavior Checklist (CBCL). ¹⁰¹ The CBCL is a 118-item parent-report measure of internalizing and externalizing problems with excellent psychometrics.

Children's Saving Inventory (CSI)¹⁰² The CSI is a 23-item self-report measure designed to evaluate child hoarding behaviors. The CSI has demonstrated strong internal consistency (a=.84-.96), as well as strong convergent and discriminant validity.

Coping Questionnaire-Parent Version (CQ-P).¹⁰³ The CQ-P is 3-item parent-rated measure that assesses their child's coping (self-efficacy in anxiety provoking situations). Specifically, this measure asks parents to report on their child's top 3 most anxiety provoking situations.

Consumer Satisfaction Questionnaire (CSQ). This measure consists of 14 items rating parents' level of satisfaction with the intervention their child received. Eleven of the items use a 7-point Likert response scale; the remaining 3 items are open-ended questions regarding the intervention.

Demographic Form. A brief demographics sheet, containing questions about marital status, family income, occupation, parental education, medical history, current medication and services etc. will provide information on a traditional set of predictors of treatment outcome.

Emotion Regulation Checklist (ERC; Shields & Cicchetti, 1997). The ERC is a 24-item other-report questionnaire that is scored on a 4-point Likert scale (1 = never; 2 = sometimes; 3 = often; 4 = almost always). It was designed to be completed by an adult who knows the child well, such as a parent (Shields & Cicchetti, 1998). The ERC assess parental perceptions of the child's emotion regulation and emotion lability.

Expectancy Rating Questionnaire (ERQ).¹⁰⁵ The ERQ will be given to parents at screening and after the adolescent's 4th therapy visit to assess treatment expectancy and credibility.

Family Accommodation Scale-Anxiety (FAS-A). The FAS-A is a parent self-report that measures family accommodation in children with anxiety disorders. This nine item measure uses a 5-point Likert-type scale that assess how often accommodation occurs and displayed high internal consistency.

The HiPIC¹⁰⁷ includes 144 items grouped into 18 facets that are hierarchically organized under the higher order factors. Parents will be instructed to describe the child by the way he or she has most often behaved over the last year by indicating on a 5-point Likert-type scale the degree to which each statement was characteristic of the child to be assessed, with scale anchors labeled as barely characteristic, slightly characteristic, more or less characteristic, characteristic, and highly characteristic. The HiPIC's robust factor structure and high internal consistencies of domains and facets have been documented in various studies with clinical and nonclinical samples.¹⁰⁸⁻¹¹¹ It will be used as a predictor of treatment outcomes.

MASC-P. ¹¹² The MASC-P is a parent-report version of the MASC with excellent psychometric properties ¹¹³, and treatment sensitivity in ASD populations. ¹¹⁵, ¹¹⁶.

Parent Expectancies for Therapy Scale (PETS). ¹¹⁷ The Parent expectancies for therapy scale (Kazdin & Holland, 1991) is a 25-item self-report measure that uses a 5-point scale to indicate the level of parent

expectancies (from low to high with 1= low and 5=high expectancy) for treatment in such domains as credibility of therapy, magnitude and rate of change likely to occur as a result of treatment, and the structure and amount of parental involvement that may be required by the treatment. This will be given at baseline assessment only.

Quality of Play Questionnaire: Parent (QPQ-P). ¹¹⁸ The QPQ-P is a parent-rated measure that assesses their child's play with peers during play dates. It contains 19 items that measure the child's type of play and interaction as well as the frequency of play dates.

Short Sensory Profile (SSP).¹¹⁹ The SSP is a 38-item parent report form that assesses children's ability to process sensory information.

Social Responsiveness Scale (SRS-P). ¹²⁰ The SRS-P is a 65-item scale measuring severity of autism spectrum symptoms (e.g., social awareness, autistic preoccupations) with excellent psychometrics. ^{44, 121}

Child-Report Measures:

Interviewers will read all items to the children (as children read along) to ensure understanding of item content. 115

Abeer Children Dental Anxiety Scale (ACDAS).¹²² The ACDAS is a measure of dental anxiety in children that employs a cognitive component. It is a 19 item scale that can be administered to children as young as 6. The ACDAS demonstrated excellent intra- and inter reliability, good concurrent validity, good discriminant validity and generalizability in the pilot trial.

Asher Loneliness Rating Scale (ALS).¹²³ The ALS is a self-report questionnaire that assesses children's perceptions of friendship quality and loneliness; this measure discriminates among children with autism and typically developing children ¹²⁴ and have strong psychometrics.¹⁸

Big Five Questionnaire-Children (BFQ-C). The BFQ-C is a 65-item questionnaire for children and adolescents developed by Barbaranelli and colleagues (2003). Children will be asked to complete this measure about themself using a Likert scale (1= Disagree strongly; 5= Agree strongly) based on how much they agree with statements made regarding their personalities. The items are written in accordance with the "Big Five" personality factors of Openness (e.g. "I like to create new games and entertainments", "I would like very much to travel and to know the habits of other countries"), Conscientiousness (e.g. "Your child likes to keep all of his/her school things in order", "Your child plays only when he/she has finished his/her homework"), Extraversion (e.g. "I like to joke", "I easily makes friends"), Agreeableness (e.g. "If someone commits an injustice towards me, I forgive that person", "I trust others"), and Neuroticism (e.g. "I easily get angry", "I am sad"). It will serve as a predictor of treatment outcome.

Coping Questionnaire-Child Version (CQ-C). ¹⁰³ The CQ-C is 3-item self-report measure that assesses coping (self-efficacy in anxiety provoking situations). Specifically, this measure asks children to report on the top 3 most anxiety provoking situations.

Negative Affectivity Self-Statement Questionnaire (NASSQ). ¹²⁷ A modified version (33 items) of the NASSQ will be used in the study. This version contains the items that significantly separated youth with an anxiety disorder from youth that did not meet criteria for an anxiety disorder. The NASSQ is a child-rated measure that assesses anxious and depressed self-statements. The NASSQ has demonstrated acceptable

psychometric properties. 127, 128 129, 130

Peer Victimization Scale (PVS).¹³¹ The Peer Victimization Scale is a child self-report used to identify kids that are being bullied. Children who score higher on this measure indicate poor self-esteem and competence as well as greater depression. It has demonstrated concurrent validity as a measure of peer victimization.

Revised Children's Manifest Anxiety Scale: Second Edition (RCMAS-2).¹³² The RCMAS-2 is a 49 item child self-report that measures different categories of anxiety (general, manifest or trait). The measure is presented in a yes/no format and consists of a Total Anxiety scale, three anxiety subscales and a Defensiveness scale. There is evidence supporting the construct validity of this measure and a test score stability coefficient of .64 to .76 was reported for a 1-week test-retest interval ¹³³.

Satisfaction/Expectancy Measures.

Therapeutic Alliance Scale for Children-Revised (TASC-R). The TASC-R is a 4-point Likert-type child; parent-; and therapist- reported questionnaire that has 12 items measuring child-therapist and parent-therapist therapeutic alliances during treatment. The 12 items are written statements. For example, a written statement for a child would be "I like spending time with my therapist" and would have four choices to circle with 1 = not like you; 2 = a little like you; 3 = mostly like you; and 4 = very much like you. The TASC-R measures two constructs of affect towards therapy: bond and negativity. Cronbach's alpha internal consistency for bond and negativity are .72 and .74 respectively. The TASC-R has been used to show that child-therapist alliance predicts therapeutic change in both therapist and child measures of child improvements (Kazdin, Marcian, & Whitley, 2005).

Expectancy Rating Questionnaire (ERQ).¹⁰⁵ The ERQ will be given to parents at screening and after the child's fourth therapy visit to assess treatment expectancy and credibility.

Treatment Adherence and Differentiation Measures.

CBT Checklist (CBTC).¹³⁵ This 24-item measure evaluates therapist treatment integrity. More specifically, the CBTC assesses manual adherence, treatment implementation, and overall skill in CBT. The supervisor will complete this form on a weekly basis.

Supervisor Rating Form (SRF).¹³⁶ The SRF is a 30-item measure completed by the CBT supervisor that assesses the supervisor's global impression of the therapist's CBT competence and in-session style. The supervisor will complete this form following the therapist's last session with his or her final study participant.

Maintaining IE Blind. Clinicians and participants cannot be blinded to treatment assignment. Accordingly, IEs will be employed to provide unbiased information on the differential efficacy of treatments. Children and their families will be provided with both written and verbal reminders prior to each assessment, emphasizing that they not disclose treatment-identifying information to the IE. IEs will not attend clinical supervision meetings, will have an office location separate from where clinical services are provided, and will be trained to avoid any discussion of treatment programs with families. They will have no contact with families other than the assessments. However, because all youth are receiving treatment, seeing the child in clinic will not unblind the IE.

Analytic Design

Specific Analyses for the Individual Study Aims: Aims 1-2: For Primary Aim 1, to model anxiety symptoms, we will use the PARS as the dependent measure in a mixed effects regression with condition as the betweensubject factor, time (Screening, Mid-treatment, Post-Treatment) as the within-subject factor and a Condition x Time interaction, with the latter used as evidence for differential rates of change. For the dichotomous outcome, treatment response (Aim 2), we will also use mixed effects regression, this time with a logistic link, with treatment condition, time (here Mid-treatment and Post-Treatment), and a Condition x Time interaction. Our primary interest is in the contrast at the end of acute treatment. The relevant continuous assessment measures for Aim 2 are described in detail in section C.5. (e.g., POPE, SRS); these scales will be assessed with the same model as in Aim 1. Aim 3: For continuous outcomes, the models of Aims 1-2 will be refit for responders only, adding the 6-month follow-up time point. Within-subjects contrasts between the follow-up time point and screening will allow us to test whether and when subjects remain significantly improved post-treatment. Evidence of deterioration (e.g., increased symptoms) over the follow-up period will also be of interest. Since all subjects in this analysis are by definition responders at treatment conclusion, we will use mixed effects logistic regression to model the likelihood of relapse or recurrence over the follow-up period. We will also report the proportions of subjects within each treatment arm who ever relapse or experience recurrence. Aim 4: To examine moderation, the interaction term between treatment condition and ASD severity will be used to examine changes over time for the continuous (PARS scores) and categorical outcomes (responder status; CGI-I). Significant interactions will be followed up by stratifying on treatment condition and examining parameter estimates, with 95% CI, for ASD severity and the outcomes. Exploratory Aim 5: Testing the mediation hypothesis requires that the direct path is meaningfully attenuated when the mediator is in the model and is also a significant predictor

of outcome. Significant effects yielded in tests of Aims 1-2 will be further evaluated by including the midtreatment mediator variables specified in B.2 in separate linear regression models and will employ bootstrapped estimates of the indirect effects.¹⁴¹ Aim 6: The same analytic plan for tests of moderation will be applied with select potential moderators.

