The considerable mental health need among children with ASD and clinically distressing anxiety is a widespread problem in need of attention. The proposed project advances the field by providing a rigorous test of efficacy of personalized CBT for anxiety in ASD against standard practice CBT for anxiety by addressing the following: (1) The study will be adequately powered to test the primary and secondary hypotheses. By employing a condition that represents standard CBT (i.e., Coping Cat), the study will answer the question of whether CBT personalized to the needs of youth with ASD and anxiety outperforms standard CBT.^{72, 73} (2) The trial will include multi-method outcome measurement, including measures of anxiety valid in ASD samples, and measures of functioning independent of anxiety severity.

(3) An a priori moderator will be tested, and other moderators will be explored. (4) A multisite plan, with therapy supervision provided by study personnel other than PIs/treatment developers, provides information on the portability of treatment and enhances generalizability of findings.

Specific Aims:

- Aim 1: To evaluate differential change over time in anxiety symptoms and response rates for the treatment conditions compared to each other and relative to a treatment as usual (TAU) control group.
- Aim 2: To examine the durability of treatment gains for youth who are deemed as treatment responders.
- Aim 3: To identify patient factors that are linked with differential treatment response such as the interaction between treatment condition and ASD severity on outcome measures post-treatment.
- Aim 4: To explore whether treatment reductions in anxiety mediate improved autism symptoms and whether treatment related reductions in autism symptoms mediate improved anxiety

Research Plan:

Overview

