psychotherapy (unless the dose is lowered because of side effects). If the child is on a medication, she or he can remain on it at its current dose. While in their arm, children will not be able to continue or initiate psychosocial interventions (psychotherapy, certain types of social skills training, applied behavior analysis targeting anxiety).

Initial Phone Screen. Individuals who meet basic eligibility requirements during the phone interview and remain interested will be invited for a screening visit, at which point a project staff will obtain informed consent from the parent.

Assessment Timeline. Participants will be randomized following screening to receive 16 weeks of BIACA, standard practice CBT, or to the 16-week TAU group. There is a 45% chance of being randomized to BIACA, 45% chance of being randomized to standard practice CBT, and 10% chance of being randomized to the TAU control (who will have their choice of interventions following the TAU phase). The Mid-treatment assessment will be done after session 8 or week 8 depending on condition. Within one week of the final treatment session or week 16, patients will complete the Post-treatment assessment. Youngsters randomized to a treatment condition will complete 6-month follow-ups. Consistent with other NIH-funded multimodal trials, families will be seen every four weeks for booster sessions during the Follow-up. Non-responders at Post-treatment will not be required to adhere to limited intervention services during the follow-up phase and will be provided with community treatment referrals (at cost to the family). If families deny the suggested maintenance plan for the follow-up phase (i.e. limited intervention services and monthly CBT sessions), a follow-up assessment will still be conducted. These families will be distinguished from those who adhere to the maintenance plan. If participants do not meet inclusion for the study, their baseline data will be kept and used in data analysis.

Treatment Conditions

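### The only specified 6-month analysis is confined to post-treatment responders, so any difference between BIACA and Coping Cat read from it is not a randomised comparison

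*Combined protocol and SAP*

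**What the plan says.** The durability aim is stated for responders: "To examine the durability of treatment gains for youth who are deemed as treatment responders". It is Aim 2 in the Specific Aims list and Aim 3 in the Analytic Design; the analysis-section number is used here.

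The Aim 1 model for PARS has condition as the between-subject factor, with "time (Screening, Mid-treatment, Post-Treatment) as the within-subject factor and a Condition x Time interaction". It stops at Post-treatment. Under Aim 3, "the models of Aims 1-2 will be refit for responders only, adding the 6-month follow-up time point". Three things then follow in the text:

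- The contrast named for continuous outcomes is within-subject: "Within-subjects contrasts between the follow-up time point and screening".
- For relapse, "we will use mixed effects logistic regression to model the likelihood of relapse or recurrence over the follow-up period". No condition term is named.
- Relapse is summarised by arm: "We will also report the proportions of subjects within each treatment arm who ever relapse or experience recurrence".

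Data collection is wider than this. The Assessment Timeline says "Youngsters randomized to a treatment condition will complete 6-month follow-ups", with no restriction to responders. The same paragraph adds that "Non-responders at Post-treatment will not be required to adhere to limited intervention services during the follow-up phase". The power section claims 80% power for a group difference of d = .53 at 6 months and expects 57 participants per CBT arm then. The opening of the Analytic Design commits in general terms to an intention-to-treat analysis of all subjects.

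**The concern.** Response at Post-treatment is an outcome, and the trial is designed to find that BIACA changes it. Once the analysis is limited to children who responded, the two groups are no longer those formed by randomisation. The Background itself gives a reason for different selection: it expects BIACA's advantage to grow with ASD severity, so Coping Cat responders may have milder ASD than BIACA responders.

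Selection also brings regression to the mean. Children chosen for a good score at Post-treatment tend to score less well later, even if nothing has changed in their arm. The arm with fewer responders is selected further into its upper tail and falls back more. A reader of the refitted Condition x Time terms, or of two relapse percentages side by side, could take that for a difference in durability.

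At stake is the trial's only evidence on whether one treatment holds its effect better than the other. The randomised groups are followed to 6 months, but no analysis that would use them is written down.

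**Working it through.** **1. The plan's own 6-month figure.** For two equal groups with unit SD and two-sided α = .05, power = Φ(d/√(2/n) − 1.96).

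- n = 57, d = .53: .53/√(2/57) = 2.83, so power = Φ(0.87) = 0.81 (0.80 with the noncentral t).

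The stated 80% is reproduced, but for 57 children per arm, which is the expected count of all retained participants. It is not a count of responders. (The stated attrition would give 90 × .90 × .85 = 68.9 rather than 57; the plan's 57 is used below.)

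**2. The same comparison in responders.** The pilot BIACA response rate is 75-79%, and the power section considers a 30-point difference. Taking 75% versus 45% gives 57 × .75 = 42.8 and 57 × .45 = 25.7 responders. The detectable difference at 80% power is 2.80 × √(1/n₁ + 1/n₂):

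| Set | n per arm | Detectable d |
|---|---|---|
| All retained | 57 / 57 | 2.80 × √(2/57) = .52 |
| Responders only | 42.8 / 25.7 | 2.80 × √(1/42.8 + 1/25.7) = .70 |

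**3. What selection alone produces.** Assumptions: bivariate normal outcome with unit SD, one response cut for both arms, correlation r between Post-treatment and 6 months, and no true mean change in either arm. The value r = .5 is the plan's generic planning correlation. With response rate p and z = Φ⁻¹(p), responders lie on average φ(z)/p above their arm mean.

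- p = .75: φ(z)/p = 0.424.
- p = .45: φ(z)/p = 0.880.

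If the selecting variable and the analysed variable are the same, the fall-back is (1 − r) × φ(z)/p. At r = .5 this is 0.21 SD for BIACA and 0.44 SD for Coping Cat, a gap of 0.23 SD.

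That is an upper illustration, because response is defined on CGI-I while the continuous outcome is PARS. The gap is then (ρ_Post − ρ_6mo) × (0.880 − 0.424), where ρ is the correlation of Post-treatment CGI-I with PARS at each time. The documents give no such correlations, so these are assumed:

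| ρ at Post, at 6 months | Gap |
|---|---|
| .7, .6 | 0.10 × 0.456 = 0.05 SD |
| .7, .5 | 0.20 × 0.456 = 0.09 SD |
| .8, .5 | 0.30 × 0.456 = 0.14 SD |
| .7, .35 | 0.35 × 0.456 = 0.16 SD |
| .7, .7 | 0 |

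**4. Apparent relapse.** The plan gives no definition of relapse. Taking it as falling back below the response cut, apparent relapse = 1 − P(above the cut at both times)/p.

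| Response rates | r | BIACA | Coping Cat |
|---|---|---|---|
| 75% vs 45% | .5 | 1 − .620/.75 = 17% | 1 − .285/.45 = 37% |
| 75% vs 45% | .7 | 13% | 28% |
| 75% vs 60% | .5 | 17% | 27% |
| equal rates | any | same | same |

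**5. If an arm test were run.** This was simulated with 10,000 trials, 57 per arm, 77% versus 47% response, r = .5 and no true deterioration. A nominal 5% test in responders rejected in about 47% of trials for relapse, and in 18% for change when selection and outcome are the same variable. The same change test in everyone followed up rejected in 5.2%.

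**The case against.** The strongest reply is that Aim 3 does not set out to compare arms. Its named contrast is follow-up against screening within children, its relapse model lists no condition term, and the aim is worded around responders. Relapse can only be described in children who have responded. All of this stands. A reader might infer from the plan that it tests BIACA against Coping Cat for durability; the text does not say so. What remains is that the refitted models contain Condition x Time and that relapse is tabulated by arm, with no warning against reading the difference causally.

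A reader might also infer that a randomised 6-month comparison was never intended. That goes too far as well. The power section gives a 6-month group difference, and the general intention-to-treat commitment covers all subjects. Such a comparison is contemplated but not specified.

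On size, the 30-point gap is a detectability statement rather than a forecast, the 75% and 45% pair is an assumption, and a stricter relapse definition would give other percentages. The direction is not fixed either: milder ASD among Coping Cat responders could make that arm look more durable.

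Finally, non-responders are released from the service limits, so an all-randomised 6-month estimate includes later outside care, possibly more in one arm. That is a real cost, but the estimate is still a comparison of randomised groups.

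**Conclusion.** The point holds in this form: the one 6-month analysis that is written out uses a subset defined after randomisation, while the population that is followed up, and on which the 6-month power claim rests, has no specified analysis. On the plan's 57 per arm, a responders-only arm comparison has a detectable d of about .70, against .52 for all retained children.

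The spurious differences are illustrative. Apparent relapse of 17% versus 37% rests on a bivariate normal outcome, r = .5, response of 75% versus 45%, no true change after Post-treatment, and relapse as crossing back over the response cut. The continuous artefact is at most 0.23 SD in that scenario, and about 0.05-0.16 SD for CGI-I selection with a PARS outcome under the assumed declining correlations. With equal response rates this between-arm artefact is zero. This concerns a secondary aim; it should be put right, and it does not touch the primary analysis at Post-treatment.

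**What to change.** 1. Add the 6-month time point to the PARS mixed model for all children randomised to BIACA or Coping Cat, and name the between-arm contrast at 6 months.
2. Report sustained response, meaning responder at Post-treatment and at 6 months, as a proportion of all randomised in each CBT arm, and state how missing 6-month status is handled.
3. Keep the responders-only models and the relapse proportions as within-arm description, with no between-arm test and a sentence saying that the subset is not randomised.

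The cost is plan wording and limited extra analysis of data already being collected; no new visits are needed. The all-randomised estimate will include community care taken up by non-responders, perhaps unequally by arm. That should be stated beside the result, and the service-use interview (SACA) could be used to describe it if it is given at follow-up.
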